### Exclusion Criteria:

1. Hypersensitivity, allergy, or significant reaction to any ingredient of the study drug, lidocaine, or latex.

2. Any disease, diagnosis, or condition (medical or surgical) that, in the opinion of the Principal Investigator, would place the subject at increased risk (active gynecologic disease in which increased tone would be detrimental e.g., uterine fibroids with ongoing bleeding and adenomyosis as reported on history), compromise the subject's compliance with study procedures, or compromise the quality of the data.

3. Women who are pregnant (positive result for serum pregnancy test at screening visit), women who are currently nursing or lactating, or those who have delivered within 2 years.

4. Pain treatment that includes spinal cord stimulators, chronic intrathecal drug therapy, or oral opioid treatment for > 3 months at a current dose of > 100 mg morphine per day or equivalent.

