## Protocol

### **Efficacy of Intrathecal Oxytocin in Patients with Neuropathic Pain**

**GOAL:** Determine the effect of intrathecal oxytocin on pain and areas and intensity of hyperalgesia and allodynia in patients with chronic neuropathic pain.

**METHODS:** Equal numbers of healthy men and women will be recruited. On a day at least 3 days before study, patients will come to the CTSI Clinical Research Unit (CRU) to review the informed consent, confirm eligibility criteria, and be trained to rate pain in response to heat applied to an area of normal skin without ongoing pain using a Peltier controlled thermode, and to rate pain in response to 225 mN von Frey filament testing within the area of hyperalgesia, if present.

Subjects will come to the CTSI CRU at least 3 days later and be randomized into one of 2 groups of 20 subjects each to receive, in a double-blind manner, intrathecal saline or intrathecal oxytocin, 100 µg. The solutions will be prepared and dispensed to this institution under IND approval and regulation from the Food and Drug Administration and will be released to the investigators through the research pharmacy at Wake Forest School of Medicine. Following subject rating of their ongoing pain and mapping of areas of allodynia and hyperalgesia, as well as rating of pain by a 225 mN von Frey filament applied in the area of hyperalgesia, an intrathecal injection of the study solution in a 3 ml volume will be performed via a #27 or #25 Whitacre needle inserted in a lower lumbar interspace. Subjects will rate their ongoing pain and that from the von Frey filament in the area of hyperalgesia, and we will map the areas of hyperalgesia and allodynia at 30, 60, 90, 120, 180, and 240 min after injection. Subjects will return a second time to the CTSI CRU at least 1 week after the first study session and the same procedures will be performed, except that they will receive the other intrathecal study drug solution (e.g., if they received saline on study session 1, they will receive oxytocin on study session 2).

We will abandon an individual participant's study and schedule another participant to receive the same randomization, should we be unable to successfully place the spinal needle to inject study solution. In our experience, this occurs in less than 10% of participants. Subjects will be recruited at Wake Forest School of Medicine pain clinics, and Orthopaedic and Podiatry

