## **STUDY DESIGN**

Inclusion Criteria: We request permission to study up to 44 subjects so that we will have 40 evaluable subjects.

1. Male or female  $\geq 18$  and  $< 70$  years of age, with a BMI  $< 40$ .
2. Presence of neuropathic pain for  $> 6$  months, with primary pain area below the umbilicus.

We will focus recruitment efforts on low back pain with a neuropathic component to the lower extremities, but will accept other causes of neuropathic pain.

3. Female subjects of child-bearing potential and those  $< 1$  year post-menopausal, must be practicing highly effective methods of birth control such as hormonal methods (e.g., combined oral, implantable, injectable, or transdermal contraceptives), double barrier methods (e.g., condoms, sponge, diaphragm, or vaginal ring plus spermicidal jellies or cream), or total abstinence from heterosexual intercourse for a minimum of 1 full cycle before study drug administration.

4. Blood pressure (systolic 90-150 mmHg; diastolic 50-90 mmHg) resting heart rate 45-100 beats per minute.

5. All subjects must be vaccinated against SARS-CoV-2, with proof via vaccination card or the NC HHS form.

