### **RANDOMIZATION GROUPS**

A computer generated randomization will be used to determine the group for each subject. Subjects will be randomized to receive an intrathecal injection of the saline placebo or 100 µg oxytocin on the first study visit, with the other on the second.

**Study Visit 1:** The participant will report to the CTSI Clinical Research Unit (CRU) at least 3 days prior to study visit 2. The participant will review and sign the Informed Consent. After informed consent is adequately obtained, a detailed medical history will be obtained from the participant, female participants will have blood drawn and sent to the laboratory to determine pregnancy status. Participants will be trained to estimate pain quantitatively using a 2 cm^2 peltier controlled thermode (TSA®) applied to an area of normal skin outside the area of ongoing pain. Typically, the participant is exposed to temperatures between 38 and 51 C using a random staircase method.

During this training period, the participant's blood pressure, heart rate, and peripheral oxyhemoglobin saturation will be recorded. A 12 Lead electrocardiogram (ECG) will also be performed.

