### **Study Visit 2**

On the second visit, the participant will report to the CTSI CRU in the morning. A peripheral intravenous catheter will be inserted into a vein in an upper extremity and lactated Ringers solution infused at 1.5 ml/kg/hr for the duration of the study. After obtaining baseline measures the subject will be placed into a lateral position and one of the investigator physicians will insert a #25 or #27 Whitacre spinal needle in a lumbar interspace using a sterile technique. After obtaining clear, free-flow CSF, a 2 milliliter sample of CSF will be obtained and stored for future use under IRB Protocol: 00003383, the sample will be stored with a unique identifier.

Oxytocin, 100 µg in a 3 ml volume, diluted with sterile normal saline, or a 3 ml injection of sterile normal saline (placebo) will then be injected over 30 seconds. Oxytocin will be prepared by Med Solutions Compounding, Winston-Salem, NC for research study purposes only. The spinal needle will be removed and the volunteer placed supine with the head of the bed elevated for the next portion of the study. Ongoing pain, pain to 225 mN von Frey filament application in the area of hyperalgesia, and areas of hyperalgesia and allodynia will be determined at 30, 60, 90, 120, 180, and 240 min after spinal injection. Blood samples (5 ml) will be obtained at 10, 20, 40, and 75 min after spinal injection by aspiration from the indwelling catheter, plasma will be prepared from the samples and frozen for subsequent analysis for oxytocin content. If blood cannot be obtained from the catheter we will not collect samples.

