#### Completion of Day 2 Assessment

1. Vital signs are within 20% of those on admission to the CRU
2. He or she can ambulate without difficulty (no motor, balance affects).
3. Someone other than the subject will take the subject home (requirement for participation).
4. Subject promises to stay home where he or she can be contacted by telephone (requirement for participation).

We will instruct the subject to call us, providing beeper and telephone numbers of the research nurse and the investigators should he have any questions or problems. The research nurse will call the subject at 6 hours and 12 hours post-spinal study drug injection inquiring about any perceived problems.

Study Visit 3: Approximately 24 hours after the spinal oxytocin injection the subject will report to the CTSI CRU to have a blood sample drawn for a Basic Metabolic Panel to assess serum sodium levels.

Study Visit 4: At least one week after Study Visit 2 the subject will return to the CTSI CRU for intrathecal injection of the cross over study solution. All procedures will be the same as Study Visit 2.

Study Visit 5: Approximately 24 hours after the spinal oxytocin injection the subject will report to the CTSI CRU to have a blood sample drawn for a Basic Metabolic Panel to assess serum sodium levels.

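### Pregnancy is tested once, at screening, and no repeat test or maximum interval is stated before either intrathecal injection

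*Combined protocol and SAP*

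**What the plan says.** - **Exclusion.** Exclusion Criteria, item 3, bars pregnant women and gives the means of establishing it in brackets: "Women who are pregnant (positive result for serum pregnancy test at screening visit".
- **Test.** Under RANDOMIZATION GROUPS, the Study Visit 1 paragraph says that "female participants will have blood drawn and sent to the laboratory to determine pregnancy status". No other pregnancy test appears in the protocol.
- **Interval to the first injection.** Study Visit 1 takes place "at least 3 days prior to study visit 2". The Methods paragraph of the Protocol section agrees: "Subjects will come to the CTSI CRU at least 3 days later".
- **Interval to the second injection.** Under Completion of Day 2 Assessment, Study Visit 4 reads: "At least one week after Study Visit 2 the subject will return to the CTSI CRU for intrathecal injection of the cross over study solution".
- **Procedures on injection days.** The Study Visit 2 section goes from the intravenous line and baseline measures to needle placement ("After obtaining baseline measures the subject will be placed into a lateral position"). It lists no pregnancy test. For Study Visit 4 the protocol says only "All procedures will be the same as Study Visit 2".
- **Contraception.** STUDY DESIGN, inclusion criterion 3, requires highly effective birth control in women of child-bearing potential and those less than one year past menopause, "for a minimum of 1 full cycle before study drug administration".

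**The concern.** Pregnancy status is verified on a day when no study drug is given and is not verified again on either day when it is given. The crossover makes this matter more than it would in a single-dose trial. Each completer receives oxytocin once, and those randomised to saline first receive it at Study Visit 4, the dosing visit furthest from the test. Both intervals are minima only, so any delay in scheduling lengthens the unverified period without limit.

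What is at stake is participant safety rather than the analysis. The protocol itself regards increased uterine tone as a possible hazard: exclusion 2 gives, as an example of increased risk, active gynecologic disease in which raised tone would do harm. A pregnancy exclusion that is not re-checked before exposure gives less protection than the sponsor evidently wants.

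**Working it through.** The plan states no figure on this point, so there is none to reproduce. The check has three parts.

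**1. Age of the test at each injection**

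| Step | Minimum | Maximum stated |
|---|---|---|
| Visit 1 (test) to Visit 2 (first injection) | 3 days | none |
| Visit 2 to Visit 4 (second injection) | 7 days | none |
| Visit 1 to Visit 4 | 3 + 7 = 10 days | none |

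**2. Could anything else in the plan reveal a pregnancy?**

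- Blood at the injection visits is taken for plasma oxytocin (10, 20, 40 and 75 minutes after injection).
- Blood at Visits 3 and 5 is for a Basic Metabolic Panel, to check sodium.
- Symptom questioning on the injection day covers sedation, anxiety, nausea, bladder symptoms, weakness and similar items.
- Calls at 6 and 12 hours ask about problems in general. Later follow-up asks about neurologic symptoms, headache and other complaints.

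A woman might volunteer that she is pregnant at one of these contacts, but none of them is a test and none asks the question.

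**3. Size**

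Inputs from the documents: 40 evaluable participants; women expected to be 40 to 60% (Minority, Gender, and Children Participation); two randomised orders of 20 each (Methods).

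- Women: 0.4 × 40 = 16 to 0.6 × 40 = 24.
- Women given oxytocin at Visit 4: about half, 8 to 12. This is an expectation only, since no stratification by sex is stated. It also counts women who are not of child-bearing potential, so it is an upper figure.

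Assumptions, because the documents give neither: contraceptive failure of 1 to 10% per year, and a test-to-injection gap of 10 days (the minimum) or 60 days (an illustrative delay).

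Chance of conception per woman = annual rate × days / 365. Expected cases = women × chance.

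| Gap | Chance per woman | Expected cases, 8 to 12 saline-first women |
|---|---|---|
| 10 days | 0.01 × 10/365 = 0.03% to 0.10 × 10/365 = 0.27% | 8 × 0.00027 = 0.002 to 12 × 0.0027 = 0.03 |
| 60 days | 0.01 × 60/365 = 0.16% to 0.10 × 60/365 = 1.64% | 8 × 0.0016 = 0.01 to 12 × 0.0164 = 0.2 |

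Women given oxytocin first add less, because their gap is shorter. At the 3-day minimum they add at most 12 × 0.10 × 3/365 = 0.01. If their gap were also 60 days, the trial total would still be at most 2 × 0.2 = 0.4.

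**The case against.** **Eligibility.** A reader might infer that a woman who conceives after screening still satisfies every criterion, so that the protocol in effect permits dosing her. The documents do not support that. Item 3 excludes pregnant women, and the bracket can fairly be read as saying how pregnancy is established at entry, not as limiting the bar to that day. Exclusion 2 also lets the investigator exclude anyone whose condition raises her risk. The gap is in detection, not in eligibility.

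**Contraception.** A reader might also infer that the contraception rule ignores the time between injections. It need not. Both sessions involve a blinded study solution, so one full cycle before study drug administration can be read as applying to each injection. At a one-week spacing, the cycle before the second injection contains the whole interval. What stands is that the wording does not settle this, and that contraception prevents pregnancy without detecting it.

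**Other protection.** Nor is item 3's pregnancy test the only safeguard against a uterine effect. Exclusion 2 addresses uterine tone, and item 3 also covers nursing women and recent delivery.

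**Usefulness of the test.** A conception within the 10-day minimum may be too recent for a point-of-care test to show. This limits the benefit at the shortest spacing. A repeat test still helps when visits slip, helps with a pregnancy too early to show at screening, and stops the undetected period from growing without limit.

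**Limits of the text.** The Visit 2 section is not an exhaustive list: baseline vital signs and local anaesthesia are described in other sections. The consent pages are not in the text reviewed and may tell participants to report a pregnancy. The finding is therefore that no repeat test is stated, not that none would ever be done.

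**Conclusion.** The concern holds as a gap in detection. One test is scheduled, at least 3 days before the first injection and at least 10 days before the second, with no upper limit and no stated repeat. Anyone following the written plan exactly could give oxytocin to a woman whose pregnancy had not been noticed, and the exposure is greatest for those who receive saline first.

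The intervals come from the documents and involve no assumption. The size does: the failure rates and the 60-day gap are assumed, the split of women by order is only expected, and the number of child-bearing potential is unknown. Under every combination shown, the expected number of cases is well below one. The documents therefore do not support any inference that the trial is likely to expose a pregnancy. The case for change rests on an inexpensive safeguard missing at the point of exposure, and it is a recommended amendment rather than a bar to the trial.

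**What to change.** 1. Add a point-of-care pregnancy test, read before the injection, at Study Visits 2 and 4 for women of child-bearing potential. Because the order is blinded, it belongs at both visits for every such woman.
2. Reword exclusion 3 so that it refers to a positive test at screening or before either injection.
3. State in inclusion criterion 3 that the contraception window applies to both injections and so runs through the second.

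This re-verifies an exclusion that the protocol already has. The study solutions, visit spacing, outcomes and analysis are unchanged.

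The cost is two inexpensive tests per eligible woman, a short amendment and an occasional same-day exclusion. Participants already attend the research unit on both days, so no visit is added. A very recent conception may still be missed.

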### **RANDOMIZATION GROUPS**

A computer generated randomization will be used to determine the group for each subject. Subjects will be randomized to receive an intrathecal injection of the saline placebo or 100 µg oxytocin on the first study visit, with the other on the second.

**Study Visit 1:** The participant will report to the CTSI Clinical Research Unit (CRU) at least 3 days prior to study visit 2. The participant will review and sign the Informed Consent. After informed consent is adequately obtained, a detailed medical history will be obtained from the participant, female participants will have blood drawn and sent to the laboratory to determine pregnancy status. Participants will be trained to estimate pain quantitatively using a 2 cm^2 peltier controlled thermode (TSA®) applied to an area of normal skin outside the area of ongoing pain. Typically, the participant is exposed to temperatures between 38 and 51 C using a random staircase method.

During this training period, the participant's blood pressure, heart rate, and peripheral oxyhemoglobin saturation will be recorded. A 12 Lead electrocardiogram (ECG) will also be performed.

### **Study Visit 2**

On the second visit, the participant will report to the CTSI CRU in the morning. A peripheral intravenous catheter will be inserted into a vein in an upper extremity and lactated Ringers solution infused at 1.5 ml/kg/hr for the duration of the study. After obtaining baseline measures the subject will be placed into a lateral position and one of the investigator physicians will insert a #25 or #27 Whitacre spinal needle in a lumbar interspace using a sterile technique. After obtaining clear, free-flow CSF, a 2 milliliter sample of CSF will be obtained and stored for future use under IRB Protocol: 00003383, the sample will be stored with a unique identifier.

Oxytocin, 100 µg in a 3 ml volume, diluted with sterile normal saline, or a 3 ml injection of sterile normal saline (placebo) will then be injected over 30 seconds. Oxytocin will be prepared by Med Solutions Compounding, Winston-Salem, NC for research study purposes only. The spinal needle will be removed and the volunteer placed supine with the head of the bed elevated for the next portion of the study. Ongoing pain, pain to 225 mN von Frey filament application in the area of hyperalgesia, and areas of hyperalgesia and allodynia will be determined at 30, 60, 90, 120, 180, and 240 min after spinal injection. Blood samples (5 ml) will be obtained at 10, 20, 40, and 75 min after spinal injection by aspiration from the indwelling catheter, plasma will be prepared from the samples and frozen for subsequent analysis for oxytocin content. If blood cannot be obtained from the catheter we will not collect samples.

#### Safety and Monitoring:

Assessment of Side Effects: Significant side effects are defined as changes > 30% from baseline in the mean arterial pressure, HR, or oxyhemoglobin pulse oximetry < 90. Any unexpected or serious side effects will be reported to the IRB and the FDA within 24 hrs. Peripheral oxyhemoglobin saturation, BP and HR will be measured non-invasively before and 15, 30, 60, 120, 180, 240, minutes after administering spinal oxytocin and the electrocardiogram will be monitored continuously for the duration of the study.

A monitor tracing from the ECG will be recorded at 15 minute intervals for the first hour then hourly until discharge. If either BP or HR change by > 30%, or oxyhemoglobin saturation decreases to less than 90, and require treatment, these vital signs will be repeated at 5-minute intervals until vital signs are stabilized. A screening neurologic exam along with questioning for qualitative symptoms will be performed at 45, 90, 150, 210, and 240 minutes. The screening neurologic test will consist of examining both an arm and leg for deep tendon reflexes (DTR's), light touch, extension/withdrawal strength. In addition we will ask the volunteer about other symptoms to include sedation, anxiety, nausea, GI, bladder, dizziness, extremity weakness, or any other symptom which was not specifically asked. Any symptom proffered will be categorized on a scale of the volunteer's choosing.

Treatment of Side Effects: Mean blood pressure elevations greater than 30% of baseline will be treated with labetalol 5-15 mg IV incrementally until BP elevation is less than 30% elevated. If BP elevation is judged to be due to pain following spinal oxytocin injection, we will treat pain first (at the volunteer's request) and only treat BP elevations if the volunteer has sufficient analgesia (he does not desire additional analgesia). Reductions in mean BP > 30% of baseline will be treated with incremental ephedrine 5-20 mg, IV. Heart rate (HR) reductions or elevations > 30% of baseline will be treated with incremental glycopyrolate 0.2 mg IV or propranolol 0.2 mg IV, respectively. Peripheral oxyhemoglobin desaturation (< 90) will be treated with supplemental oxygen, nasal cannula, face mask, or non-rebreathing mask depending upon the degree desaturation and the response to therapy.

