We subsequently performed several studies which suggest that spinal release of oxytocin represents the protective factor against chronic pain after childbirth. Intrathecal injection of the specific oxytocin receptor antagonist, atosiban, temporarily reverses the blockade of nerve injury induced hypersensitivity in the postpartum period in rats. Similarly, intracerebroventricular administration of the  $\alpha$ -adrenoceptor antagonist, phentolamine, which is known to block the effects of lactation on activation of oxytocin-containing neurons in the paraventricular nucleus (PVN) of the hypothalamus, also temporarily reverses the blockade of nerve injury induced hypersensitivity in the postpartum period in rats. Finally, protection against hypersensitivity from nerve injury is abruptly reversed when pups are separated from dams for 24 hr, and this is accompanied by a large decrease in oxytocin concentration in cerebrospinal fluid. Although we are currently performing more clinical and laboratory studies to further define this mechanism, these data suggest that spinal oxytocin receptor stimulation in the period immediately following delivery protects against the generation of injury-induced hypersensitivity and subsequent chronic pain.

We recently completed a Phase 1 safety study of intrathecal oxytocin and observed no serious adverse events over the dose range studied (5-150  $\mu$ g). One subject at the 150  $\mu$ g dose had transient subjective numbness in sacral dermatomes, but this was preceded by a vasovagal episode beginning just prior to spinal injection, and this did not occur in other subjects at this dose. There were no objective signs of motor or sensory dysfunction in any volunteer, and blood pressure, heart rate, sensorium, corrected QT interval and serum sodium were unaffected.

We anticipate that oxytocin will be effective after spinal injection in humans to acutely relieve chronic neuropathic pain. For these future studies, we will use a cross over, controlled and blinded study of intrathecal oxytocin in patients with neuropathic pain below the umbilicus, with primary outcome being visual analog score for pain and secondary outcomes being areas of increased pain sensation to a normally painful stimulus (hyperalgesia) and pain sensation to what previously was an innocuous stimulus (allodynia).

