### **Previous Experience in the CRU**

These investigators have, under NIH grant GM48085, regularly performed intrathecal injection studies with novel drugs for intrathecal delivery in healthy volunteers and in patients since 1990. Drugs studied include clonidine, fentanyl, neostigmine, adenosine, ketorolac and oxytocin. In addition, we have studied drugs approved for intrathecal delivery (morphine and bupivacaine) in the CRU. The most common adverse effect from these studies has been mild, transient backache and headache. Persistent headache requiring blood patch has occurred in <1% of subjects, likely reflecting the use of very small gauge (#27), pencil point spinal needles. Drug related adverse effects have included hypotension and bradycardia (clonidine), nausea (fentanyl, neostigmine), mild respiratory depression (fentanyl), transient back and leg pain (adenosine) and one episode of hypotension and bradycardia consistent with a vaso-vagal response to injection (oxytocin). The IRB and FDA recognizes that there are potential risks to these studies and has supported performance of this research in the CRU with the presence of an anesthesiologist and nurse,

appropriate monitoring, intravenous access, and immediate access to appropriate drugs for treatment.

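### No blood pressure reading is scheduled between the pre-injection value and 15 minutes, so a brief fall in pressure at injection can go unrecorded

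*Combined protocol and SAP*

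**What the plan says.** The reading times are in Safety and Monitoring: "Peripheral oxyhemoglobin saturation, BP and HR will be measured non-invasively before and 15, 30, 60, 120, 180, 240, minutes after administering spinal oxytocin". The sentence names oxytocin only. Study Visit 4 repeats all the procedures of Visit 2, so I take the schedule to cover the saline session as well.

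The same section defines the event: "Significant side effects are defined as changes > 30% from baseline in the mean arterial pressure, HR", or a saturation below 90. It adds that "the electrocardiogram will be monitored continuously for the duration of the study". If pressure or heart rate changes by more than 30%, or saturation falls below 90, and treatment is needed, "these vital signs will be repeated at 5-minute intervals until vital signs are stabilized".

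Study Visit 2 fixes the order of events: "After obtaining baseline measures the subject will be placed into a lateral position". Needle placement, CSF sampling, a 30-second injection and the turn to supine follow. Staff return for plasma samples: "Blood samples (5 ml) will be obtained at 10, 20, 40, and 75 min after spinal injection".

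Two sections describe an earlier event. Previous Experience in the CRU lists, among drug-related effects, "one episode of hypotension and bradycardia consistent with a vaso-vagal response to injection (oxytocin", with oxytocin named in brackets as the drug. Background says of the Phase 1 volunteer with transient numbness that "this was preceded by a vasovagal episode beginning just prior to spinal injection".

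**The concern.** A mean arterial pressure event needs a pressure reading before it can be counted. The plan's own history places hypotension at the injection, yet the first pressure after injection is taken at 15 minutes. A short fall that recovers by then leaves no trace in the scheduled data, and the record for that session looks clean.

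What is at stake is the completeness of the blood pressure record for a drug whose exact risks the Risks section calls unknown. The primary analysis of pain is not affected.

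**Working it through.** The plan gives no figure to reproduce here. The check is which falls in pressure contain a scheduled reading. Reading times come from Safety and Monitoring. Episode length *d* and onset time are assumptions, because the documents give neither.

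**1. Gaps.** Readings after injection are at 15, 30, 60, 120, 180 and 240 min. The intervals are 15 − 0 = 15, 30 − 15 = 15, 60 − 30 = 30, then 60, 60 and 60 min.

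**2. Onset at injection.** The episode runs from 0 to *d* and contains the first reading only if *d* ≥ 15. Episodes of 1, 2, 5, 10 and 14 min contain none; 15 or 20 min contains one. If onset is up to 2 min after injection, a 10-min fall ends by 2 + 10 = 12 min and is still missed.

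**3. Onset spread evenly over 0 to 15 min.** The 15-min reading catches onsets from 15 − *d* to 15, so the chance is min(1, *d*/15). A reading added at 10 min also catches onsets from 10 − *d* to 10.

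| *d* (min) | Current schedule | With a 10-min reading |
|---|---|---|
| 1 | 1/15 = 7% | 2/15 = 13% |
| 2 | 2/15 = 13% | 4/15 = 27% |
| 5 | 5/15 = 33% | (5 + 5)/15 = 67% |
| 10 | 10/15 = 67% | onsets 0–10 and 5–15 cover all: 100% |

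**4. What a 10-min reading cannot do.** A 5-min fall starting at injection ends at 5 min, before that reading. Only a reading soon after injection can catch it. A reading taken *m* minutes after injection catches a fall that started at injection if *d* ≥ *m*.

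**5. Onset before injection.** If the baseline measures in Study Visit 2 include the pre-injection vital signs, the unmeasured window also covers positioning, needle placement and CSF sampling. An episode that starts just before injection, as Background describes, then lies between the baseline and 15-min readings unless it persists to 15 min.

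**6. Other scheduled checks.** The ECG shows rate and rhythm only. The 5-minute repeats need a change already seen and in need of treatment. The first scheduled neurologic screen and symptom questioning is at 45 min. None of these schedules a pressure before 15 min.

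**The case against.** Four points can be made against this, and each narrows it.

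- **Heart rate can trigger a check.** A reader might infer that the 5-minute repeats start only after a scheduled reading finds a change. The text does not say so. A heart-rate change of more than 30% seen on the continuous ECG, if it needs treatment, also starts them. The earlier event included bradycardia, and Previous Experience in the CRU says an anesthesiologist and a nurse are present. A repeat of that event with a marked fall in rate, or with symptoms, would probably be noticed and measured. What remains is a brief fall without such a prompt.
- **The earlier event may not be a drug effect.** A reader might infer a known haemodynamic signal of oxytocin. The documents support only one episode, described as vasovagal. It may be the Background episode that began before any drug was given, though the documents do not link the two. Background also reports blood pressure and heart rate unaffected over 5–150 µg, and Risks reports no toxicity in Phase 1 or in over 90 hip replacement subjects. This stands: a reaction to the procedure explains the event at least as well.
- **Neither treatment is favoured.** A reader might infer a biased safety comparison. Both sessions follow one schedule, so the gap favours neither by design. Statistical Rationale plans a comparison of pain only.
- **No pressure–exposure analysis is planned.** A reader might fault the plan for not pairing pressure with plasma oxytocin. The stated goal concerns pain, hyperalgesia and allodynia, so that pairing is not something the plan has failed to deliver.

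None of this supplies a pressure reading before 15 minutes.

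**Conclusion.** The concern holds in a limited form. A fall in pressure that starts at injection, lasts under 15 minutes, and comes without a heart-rate change or symptoms that lead staff to check contains no scheduled reading. It therefore cannot be counted under the 30% mean arterial pressure definition. The one oxytocin-related event in the plan's history is of the kind that occurs in this window, whatever its cause.

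The size depends on assumed timing and length. Scheduled capture is zero for any fall under 15 minutes that starts at injection. With even onset over 15 minutes it runs from 7% at 1 minute to 67% at 10 minutes. These figures describe scheduled readings only; unscheduled checks by attending staff would raise them by an amount the documents do not allow me to estimate.

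The consequence is an incomplete safety record, to the same degree by design in both sessions. It is a modest data-collection gap worth closing because closing it is cheap.

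**What to change.** In Safety and Monitoring, keep every current reading time. At Visits 2 and 4, also record non-invasive blood pressure, heart rate and saturation (a) once the patient is supine after injection and (b) at 10 minutes, when the first blood draw is already due. Take the 10-minute reading even if the draw fails, since Study Visit 2 allows for failed draws. Readings at the 20-, 40- and 75-minute draws are optional.

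Label the added readings as safety data. The 30% limit is also tied to treatment in the same section, and this change is not meant to alter any treatment rule. The sponsor should reconcile the reading times with the 30% definition and with the event in Previous Experience in the CRU, state when the pre-injection reading is taken relative to positioning, and say that the schedule applies after either study solution.

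The cost is protocol wording and two cuff readings per session, or 2 × 2 × 40 = 160 over 40 evaluable subjects with two sessions each. With the optional draws it is five per session, or 400. The downside is slightly more cuff inflation. Neither core reading coincides with a post-injection pain rating, the first of which is at 30 minutes.
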